Percentage of patients achieving pressure support ventilation equal to 5 cmH ₂ O with PEEP equal to 5 cmH ₂ O for 2 hours (measure of weaning) by day 28 and at hospital discharge [study day: date]	
As per study protocol, CPAP (Continuous Positive Airway Pressure) is defined as use of pressure support ventilation equal to 5 cmH₂O with PEEP equal to 5 cmH₂O for 2 hours.
 
The CRF Field: "Number of attempts at weaning defined as continuous positive airway pressure (CPAP) trial (CPAP 5 cmH₂O plus PEEP 5 cmH₂O) of 2 hours duration" (in CRF Form: "Ventilation-Specific Information" in Daily assessments through extubation") counts the number of attempts at weaning as =1 each time that a CPAP 5 cmH₂O + PEEP 5 cmH₂O has been performed for 2 hours.
 
Number of patients achieving pressure support ventilation equal to 5 cmH₂O with PEEP equal to 5 cmH₂O for 2 hours (measure of weaning) by day 28
 
event = "Y" if at least one "Number of attempts at weaning defined as continuous positive airway pressure (CPAP) trial (CPAP 5 cmH₂O plus PEEP 5 cmH₂O) of 2 hours duration" >0 and date of daily collection (VSI DAT) is performed between Day 1 (date of 1st IMP intake) and Day 28.
 
otherwise event = "N" if all assessments are available (i.e., no missing values are present) between date of 1st IMP intake and Day 28 (or, in general, for all days of intubation) and they are all = 0
 
otherwise, event is missing.
 
Day 28= Day1 (date 1st IMP intake) + 27
 
Number of patients achieving pressure support ventilation equal to 5 cmH₂O with PEEP equal to 5 cmH₂O for 2 hours (measure of weaning) by hospital discharge
 
event = "Y" if at least one "Number of attempts at weaning defined as continuous positive airway pressure (CPAP) trial (CPAP 5 cmH₂O plus PEEP 5 cmH₂O) of 2 hours duration" >0 and date of daily collection (VSI DAT) is performed between Day 1 (date of 1st IMP intake) and date of discharge*.
 
event = "N" if all assessments are available (i.e., no missing values are present) between date of 1st IMP intake and Hospital discharge* and they are all = 0
 
otherwise, event is missing.
 
*date of discharge is collected in EOS; in the case it is missing it is taken from Visit date in "Hospital Discharge" .. If the subject has no hospital discharge it is assumed is because the subject was not discharged, so it is assumed that the event was during the hospitalization

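### Weaning endpoint: by hospital discharge, non-achievers with complete zero records are coded missing, and the plan does not say how missing enters the between-arm test

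*SAP*

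**What the plan says.** The derivation is in SAP 11.1.1, in the row for patients achieving pressure support of 5 cmH2O with PEEP 5 cmH2O for 2 hours. It has a Day 28 version and a hospital-discharge version.

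- **Y, both versions:** "event = 'Y' if at least one 'Number of attempts at weaning defined as continuous positive airway pressure (CPAP) trial" exceeds zero within the window. Gaps on other days do not matter.
- **N, both versions:** "if all assessments are available (i.e., no missing values are present") and every value is zero.
- **Window for N, Day 28:** from first IMP intake to "Day 28 (or, in general, for all days of intubation) and they are all = 0".
- **Window for N, discharge:** "between date of 1st IMP intake and Hospital discharge* and they are all = 0". There is no reference to intubated days.
- **Everyone else:** "otherwise, event is missing".
- **Source:** the field sits on the Ventilation-Specific Information form, "in Daily assessments through extubation". Protocol 6.1.3 agrees. The 48-hourly assessments after extubation do not include it, and it resumes only on re-intubation.
- **No discharge date:** "If the subject has no hospital discharge it is assumed is because the subject was not discharged", and the event is then taken to fall within the hospital stay. That serves Y. It sets no end date for N.

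Two other sections matter. SAP 4.10, like Protocol 9.5, keeps missing values in the denominator of percentages unless an exception is declared, and none is declared for this endpoint. SAP 7.2.1.8 compares the proportions by Fisher's exact or chi-square test and is silent on how missing patients enter it.

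**The concern.** The two codes carry different burdens of proof. One lost daily form turns a non-achiever into missing, while an achiever with another positive day is untouched. The longer a patient is ventilated, the more forms there are to lose, and ventilation time is what the drug is meant to shorten.

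The discharge version adds a separate problem: it asks for daily values on days when the form is not collected. The Day 28 clause about intubated days shows that the authors saw this difficulty, but they solved it in only one of the two rules. Two programmers could code the discharge version differently.

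At stake are the accuracy of the reported N and missing counts and, if missing patients are dropped from the test, a comparison that has lost mainly non-achievers.

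**Working it through.** The documents give no weaning rate, daily missingness or power for this endpoint, so there is no planned figure to reproduce. Every rate below is an assumption for illustration.

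**Step 1. The two rules on the same data.** Take a patient intubated Days 1 to 10, with all ten daily values zero, extubated on Day 10 and discharged on Day 20.

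| Rule | Values required | Values that exist | Code |
|---|---|---|---|
| Day 28 | the intubated days, 1 to 10 | 10 of 10, all zero | N |
| Discharge, literal | Days 1 to 20 | none after extubation | missing |

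A patient who dies in hospital with all zeros and no discharge date is N by Day 28 on the intubated-days clause, but has no closing date under the discharge rule. On the literal reading, N by discharge is left mainly to patients who leave hospital still intubated with a complete record.

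**Step 2. Neighbouring rows of the same table.** ECMO and vasoactive use come from the same daily form. There, N requires only that the last available day is at least 12, with no day-by-day completeness. The tracheostomy and LTAC rows replace a missing discharge date by the death date. The weaning row does neither.

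**Step 3. Non-achievers lost to isolated gaps (Day 28 version).** With daily missingness m, independent between days, and D intubated days, a true non-achiever keeps N with probability (1−m)^D.

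| m | D = 10 | D = 14 |
|---|---|---|
| 1% | 0.90 | 0.87 |
| 2% | 0.82 | 0.75 |
| 5% | 0.60 | 0.49 |

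**Step 4. Effect on the percentage.** Assume 60% true achievers, each with one positive day, and D = 14.

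- All patients in the denominator (SAP 4.10): 0.6 × 0.98 = 58.8% at m = 2%; 0.6 × 0.95 = 57.0% at m = 5%. Both are below the true 60%.
- Classified patients only: 0.588 / (0.588 + 0.4 × 0.754) = 66% at m = 2%; 0.570 / (0.570 + 0.4 × 0.488) = 75% at m = 5%.

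**Step 5. Effect on the test if missing is dropped.** Take 30 per arm (60 evaluable, 1:1) with 21 and 15 achievers.

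- All non-achievers classified: 21/30 against 15/30, a difference of 20 points, Fisher p = 0.19.
- One non-achiever in five keeps N (about 2 of 9 and 3 of 15): 21/23 = 91% against 15/18 = 83%, a difference of 8 points, p = 0.64.
- None keeps N: 21/21 against 15/15, and no comparison is possible.

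The loss can also differ between arms. Suppose both arms truly have 60% achievers and m = 5%, but non-achievers are ventilated 10 days in one arm and 14 in the other. The classified percentages are 0.570 / (0.570 + 0.4 × 0.599) = 70% and 75%. The arm with shorter ventilation looks worse although nothing differs in weaning.

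**The case against.** The strongest objection is the denominator. A reader might infer from the asymmetry that the weaning percentage is biased upward, or that the discharge version is close to 100% by construction. The documents do not support this for the tabulated percentage. Under SAP 4.10 and Protocol 9.5 it is Y over all FAS patients. Moving a non-achiever from N to missing changes neither numerator nor denominator, and an unrecorded positive day can only lower the figure. Where the SAP means to exclude patients it says so, as for secondary infections by discharge. This stands in full. The 66% and 75% apply only to classified patients.

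The bias in the test is likewise not established. SAP 7.2.1.8 can be read as testing the same proportions that are tabulated. That is fair, but the 4.10 rule is worded for descriptive summaries, so the test remains open. In Step 5 dropping missing patients mostly weakens the comparison; no general direction in favour of reparixin follows.

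The discharge rule could also be read as requiring only assessments that were scheduled. N would then be reachable for patients discharged alive. This is a reasonable reading, but the clause that would settle it appears in one rule and not the other. Nor does either point make N unreachable by Day 28.

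The affected group may be small. The suggested ventilation protocol (Protocol 14.4.7) disconnects patients after two hours at pressure support 5, so most extubated patients managed that way should already be Y. It is only suggested, however, and Protocol 3.3 leaves ventilation to the investigator's discretion.

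Finally, leaving an incompletely observed outcome missing is defensible in itself, and this is one of many secondary endpoints with descriptive p-values. That limits the weight of the point. It does not explain why identical data should give N by Day 28 and missing by discharge.

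**Conclusion.** The point holds as a derivation inconsistency and an unstated test rule. The differing N windows and the absence of a closing date for in-hospital deaths are in the text. That an extubated non-achiever becomes missing by discharge rests on the literal reading of the completeness condition.

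The number of patients affected cannot be taken from the documents. The reported percentage is unaffected or slightly low. The misreporting is in the N and missing counts, and the comparison is distorted only if the test drops missing patients. In that case the illustration gives 66% to 75% among classified patients against a true 60%, and a 20-point difference can shrink to 8. These sizes rest on assumed weaning rates, ventilated days, independent daily missingness and share of non-achievers still classified. Since the endpoint is secondary and descriptive, this is worth correcting because it is cheap, not because a trial conclusion depends on it.

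**What to change.** Amend the weaning row of SAP 11.1.1 and section 7.2.1.8:

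1. Limit the discharge rule to days of intubation up to discharge, as the Day 28 rule already does.
2. Where the discharge date is missing and the patient died, end the window at the death date, as in the tracheostomy and LTAC rows.
3. Score N when daily forms exist for the intubated days and none records a positive attempt, in line with the ECMO and vasoactive rows. Keep missing for patients with no daily form at all.
4. State that the Fisher or chi-square test compares Y with not-Y over all FAS patients in each arm, the same denominator as the table.

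The cost is a few lines of SAP text and the matching change in the derivation program; no new data are needed. The one drawback is that a weaning trial carried out on an unrecorded day is scored as not done. The tabulated percentage already treats it that way.

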11.1.2 Partial date conventions

Table 4: Algorithm for Treatment Emergence of Adverse Events

AE START DATE	AE STOP DATE	RULE for TEAE definition	RULE for "Treatment" / "Follow-up" study period definition for TEAE summaries
Known	Known, Partial or Missing	If AE start date < IMP start date, then not TEAE If AE start date >= IMP start date, then TEAE	If AE start date > max(Date of last IMP intake, End of Treatment) then "Follow-up", otherwise "Treatment" period.
Partial, but known components show that it cannot be on or after IMP start date	Known, Partial or Missing	Not TEAE	Not applicable
Partial, could be on or after IMP start date	Known	If AE stop date < IMP start date, then not TEAE If AE stop date >= IMP start date, then TEAE	If TEAE, then Treatment study period for TEAE occurrence.
	Partial	Impute stop date as latest possible date (i.e. last day of month if day unknown or 31 st December if day and month are unknown), then: If AE stop date < IMP start date, then not TEAE If AE stop date >= IMP start date, then TEAE	
	Missing	Assumed TEAE	
Missing	Known	If AE stop date < IMP start date, then not TEAE If AE stop date >= IMP start date, then TEAE	If TEAE, then Treatment study period for TEAE occurrence.
	Partial	Impute AE stop date as latest possible date (i.e. last day of month if day unknown or 31 st December if day and month are unknown), then: If AE stop date < IMP start date, then not TEAE If AE stop date >= IMP start date, then TEAE	
	Missing	Assumed TEAE	

NOTE: Assignment to "Treatment" or "Follow-up" study period is applicable only for TEAEs.

Standard/Forms/Template				
Title		Statistical Analysis Plan Template		
Code		Version	Effective Date	Page
PPD		01	29 Aug 2022	76 of 78

Table 5: Algorithm for Prior/Concomitant medications

MEDICATION START DATE	MEDICATION STOP DATE	RULE for prior or concomitant categorization
Known	Known	If medication stop date < date of first dose of IMP, assign as prior If medication stop date >= date of first dose of IMP, assign as concomitant
	Partial	Impute medication stop date as latest possible date (i.e. last day of month if day unknown or 31 st December if day and month are unknown), then: If medication stop date < date of first dose of IMP, assign as prior If medication stop date >= date of first dose of IMP, assign as concomitant
	Missing	Assign as concomitant
Partial	Known	If medication stop date < date of first dose of IMP, assign as prior. Impute medication start date as earliest possible date (i.e. first day of month if day unknown or 1 st January if day and month are unknown), If medication stop date >= date of first dose of IMP and start date >= date of first dose of IMP and before end of study day, assign as concomitant
	Partial	Impute medication stop date as latest possible date (i.e. last day of month if day unknown or 31 st December if day and month are unknown), and impute medication start date as earliest possible date (i.e. first day of month if day unknown or 1 st January if day and month are unknown), then: If medication stop date < date of first dose of IMP, assign as prior If medication start date >= date of first dose of IMP and before end of study day and stop date >= date of first dose of IMP, then assign as concomitant
	Missing	Impute medication start date as earliest possible date (i.e. first day of month if day unknown or 1 st January if day and month are unknown), then: If medication start date >= date of first dose of IMP and before end of study day, then assign as concomitant
Missing	Known	If medication stop date < date of first dose of IMP, assign as prior.
	Partial	Impute medication stop date as latest possible date (i.e. last day of month if day unknown or 31 st December if day and month are unknown), then: If medication stop date < date of first dose of IMP, assign as prior

Standard/Forms/Template				
Title		Statistical Analysis Plan Template		
Code		Version	Effective Date	Page
PPD		01	29 Aug 2022	77 of 78

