8.3. RECORDING OF ADVERSE EVENTS

All AEs (serious and non-serious) which occur from signature of the informed consent through patient participation in the study (last planned visit or early withdrawal date) will be collected and recorded in the eCRF. It is important that the AE dedicated section of the eCRF includes the duration of the AE (onset/resolution dates), the relationship to the drug, the severity, the outcome, the action(s) taken and relevant concomitant treatments dispensed. When possible, signs and symptoms indicating a common underlying pathology should be documented as one comprehensive event.

All AEs should be followed-up to determine the outcome of the reaction. The Investigator should follow up the event until resolution or stabilization of the condition. It is the Investigator's responsibility to assure that the patients experiencing an AE receive definite treatment for any AE, if required.

Medical conditions/diseases present before starting study treatment shall be documented in the medical history section of the eCRF; these conditions are considered AEs only if they increase either in frequency or severity once informed consent has been signed.

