8.3.3. Severity of adverse events

The Investigator will grade the severity of any AE using the definitions in the Table below. For each episode, the highest severity grade attained should be reported.

Severity of the Adverse Event

Mild	Grade 1 - Does not interfere with the patient's usual function (awareness of symptoms or signs, but easily tolerated [acceptable]).
Moderate	Grade 2 - Interferes to some extent with the patient's usual function (enough discomfort to interfere with usual activity [disturbing]).
Severe	Grade 3 - Interferes significantly with the patient's usual function (incapacity to work or to do usual activities [unacceptable])

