8.1 Adverse events

Adverse Events (AEs) started before administration of study treatment will be considered as pre-treatment; any AE started on or after the date of the administration of the first dose of study medication or started prior to the administration of the first dose and worsened in severity after the administration of the first dose will be considered as TEAE.

In case of missing or incomplete dates not allowing a direct allocation to any of the two categories of AEs (pre-treatment/TEAE), an allocation will be done according to the available parts of the onset and the end dates (Table 4 in section 11.1.2). In case of TEAE, the event can be further classified as:

1. On Treatment period, or
2. On Follow-up period

according to the available parts of the onset and the end dates (Table 4).

All AEs will be coded by SOC and PT according to MedDRA Version 25.0 (or later) thesaurus.

In addition, each AE will be graded to capture the relationship to IMP and severity. “Possible”, “Probable” and “Highly Probable” or missing relationships will be considered as related to study drug (ADR – Adverse Drug Reaction) for the summary tables. “None” and “Unlikely” relationships will be considered not related to study drug.

Pre-treatment AEs will be presented in the listings only.

TEAE summaries will be presented, displaying frequencies and percentages of patients reporting TEAEs within each SOC in decreasing order of total frequency. Along with TAEs, number of events will be reported. On each of these summaries, patients will be counted only once per SOC and, within each SOC, patients will be counted only once per PT.

The following tables and listings will be presented by treatment group:

- An overview of TEAEs including:
 - the number of patients who exhibited at least one TEAE, at least one severe TEAE, at least one serious TEAE, at least one non-serious TEAE, at least one ADR, at least one serious ADR, at least one TEAE leading to discontinuation of IMP, at least one TEAE

Standard/Forms/Template				
Title		Statistical Analysis Plan Template		
Code		Version	Effective Date	Page
PPD		01	29 Aug 2022	52 of 78

leading to discontinuation of study, at least one TEAE leading to death, at least one secondary infection TEAE by Day 28 and by hospital discharge,

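### SAP Table 4 (11.1.2) has no worsening branch and so contradicts the SAP 8.1 TEAE definition for events that start on a calendar day before IMP and worsen after first dose

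*SAP*

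**What the plan says.** SAP 8.1 gives a definition with two limbs. An event is treatment-emergent if it starts on or after the date of first dose, or if it "started prior to the administration of the first dose and worsened in severity after the administration of the first dose will be considered as TEAE". Pre-treatment events are listed but not tabulated. 8.1 then refers to Table 4 under a condition: "In case of missing or incomplete dates not allowing a direct allocation to any of the two categories of AEs".

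Table 4, in SAP 11.1.2 (not the seed-number table in 11.2, which carries the same number), is titled as the algorithm for treatment emergence. Its first row covers a known start date and has two outcomes: "If AE start date < IMP start date, then not TEAE" and "If AE start date >= IMP start date, then TEAE". Its second row, headed "Partial, but known components show that it cannot be on or after IMP start date", returns not TEAE whatever the stop date.

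SAP Table 3 defines the on-treatment and follow-up periods for TEAEs by start date.

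On recording, Protocol 8.3 collects adverse events from consent. Conditions already present before study treatment go to medical history, and "these conditions are considered AEs only if they increase either in frequency or severity once informed consent has been signed". Protocol 8.3.3 adds: "For each episode, the highest severity grade attained should be reported".

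**The concern.** The SAP holds two rules that give different answers for the same event. Take an event that starts after consent, on the day before first dose, at mild severity, and becomes severe on study drug. Under 8.1 it is a TEAE. Under Table 4 it is not. Two programmers could each follow the SAP and produce different safety tables.

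The incidence of TEAEs and serious TEAEs is a protocol safety endpoint (Protocol 7.2), so the flag matters. If Table 4 decides it, a worsened pre-dose event drops out of the overview and of the tables for all TEAEs, serious TEAEs, ADRs, events leading to IMP or study discontinuation, and events leading to death.

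The situation can arise. Events are collected from consent, screening may be on day -1, and randomization may follow screening by up to 24 hours in ventilated patients with moderate to severe ARDS.

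**Working it through.** No figure in the plan is at stake, so the check sets the two rules side by side, case by case.

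| Start relative to IMP start date | Worsened after first dose? | SAP 8.1 | Table 4 | Result |
|---|---|---|---|---|
| Known, earlier calendar day | No | not TEAE | not TEAE | agree |
| Known, earlier calendar day | Yes | TEAE | not TEAE | **conflict** |
| Partial, certainly earlier | No | not TEAE | not TEAE | agree |
| Partial, certainly earlier | Yes | TEAE | not TEAE | **conflict** |
| Known, same calendar day but before the dose | Either | TEAE | TEAE | agree |
| Known, after the dose | Either | TEAE | TEAE | agree |
| Partial and undetermined, or missing; stop date on or after IMP start, or missing | Yes | TEAE | TEAE | agree |
| Same | No | depends on the unknown start | TEAE | default that leans towards counting |

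The contradiction is therefore confined to worsened events whose start is known, or certain from the date parts available, to lie on an earlier calendar day than first dose.

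**Scope of Table 4.** By the sentence in 8.1, a known start date allows direct allocation and Table 4 is not needed. Yet Table 4's first row is written for complete start dates and accepts a complete stop date, so its content goes beyond the role 8.1 gives it. The second row does fall within that role, since it concerns incomplete dates, and it also lacks a worsening branch.

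**Study period.** Suppose 8.1 is applied and the worsened event is kept.
- Table 3, on-treatment: start on or after treatment start and no later than end of treatment. Not met.
- Table 3, follow-up: start after end of treatment. Not met.
- Table 4, period column for a known start: treatment period unless the start is after the later of last intake and end of treatment. This gives treatment period.
- Table 4, period column for the certainly-earlier partial date: not applicable.

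So the SAP gives three different answers on period. Five summaries in SAP 8.1 are split by period: TEAEs, serious TEAEs, ADRs, and those leading to IMP discontinuation or to study discontinuation.

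**Identifying worsening.** Protocol 8.3 names onset and resolution dates and severity among the recorded items, and 8.3.3 asks for the highest grade per episode. Neither document mentions a date of worsening, or tells sites to open a new record when an event that began after consent gets worse. The SAP does not say what data would show worsening.

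**Size.** The documents give no count of pre-dose events and no rate of worsening, so the number affected cannot be derived. The only arithmetic available is the weight of one patient: 66 / 2 = 33 per arm, and 1 / 33 = 3.0 percentage points. Even that shift occurs only if the patient has no other event in the same table row.

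**The case against.** The strongest reply is that 8.1 is the definition and Table 4 only a fallback. It sits under partial date conventions, and 8.1 invokes it only where dates do not allow direct allocation. For a known start date, 8.1 applies and the worsened event stays in. This stands to the extent that the loss is conditional on Table 4 being used as the operative rule. It does not remove the contradiction, because Table 4 carries an explicit row for complete dates and its certainly-earlier row has the same gap.

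Several stronger readings are tempting, and the documents do not support them:
- *All pre-dose events are excluded.* Table 4 compares dates, not times, so events earlier on the dosing day count as TEAEs. Undetermined or missing start dates count too, unless the event stopped before IMP. Screening, randomization and Day 1 may share a calendar day (SAP 3.2.2), so the exposed window is short and sometimes empty.
- *Fatal events disappear.* They would leave the TEAE-leading-to-death table. They remain in the death listing, in the death summary with proximate cause, and in all-cause mortality. IMP discontinuations and their reasons are also tabulated separately (SAP 5.3).
- *The recorded data cannot support the 8.1 rule.* Highest grade per episode does not forbid a new record on worsening, and the eCRF and its completion guide are not available here. Under the medical-history sentence in Protocol 8.3, some conditions that worsen on drug may be entered as adverse events only at worsening, which both rules would count.
- *The DMC saw incomplete tables.* Nothing here shows which flag those tables used.

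**Conclusion.** The point holds in this form. Table 4 contradicts SAP 8.1 for events known or certain to start on a calendar day before IMP start that worsen after first dose. Programmed as written, Table 4 would send them to the pre-treatment listing only and remove them from the TEAE tables. Using 8.1 alone is not a complete answer either, because Table 3 gives such an event no study period and the SAP does not say how worsening is recognised.

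The conclusion on lost events assumes that Table 4 sets the flag; the wording conflict itself needs no assumption. The number of events affected is unknown, and any estimate would be a guess about how often patients have an event in the short interval between consent and dosing and how often it worsens. This is a specific error in the SAP wording, worth correcting because it bears on a safety endpoint and costs little. It is not evidence that safety results are materially incomplete.

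**What to change.** 1. In both Table 4 rows (known start before IMP start; partial start certain to be before it), state that the event is not a TEAE unless it worsened in severity after first dose as defined in section 8.1, in which case it is a TEAE.
2. State how worsening is identified from the recorded data, given the highest-grade-per-episode instruction in Protocol 8.3.3. If no date of worsening or pre-dose grade is held, name a default, chosen while blinded, for pre-dose events still ongoing at first dose. Keep it tied to increased severity. Adding seriousness, outcome or action taken as triggers would be a new definition that goes beyond 8.1.
3. Amend the on-treatment and follow-up definitions in Table 3, and the matching column of Table 4, so that a worsened pre-dose event has one stated period.

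The cost is SAP wording and a small programming change. The downside is that, where the date of worsening is not recorded, a conservative default may over-count a few events as treatment-emergent. New eCRF instructions are probably too late: SAP Final 2.0 is dated 30 July 2025 and the last patient's last visit was planned for February 2025. If the tables have already been run, the clinical study report should say which rule set the flag and list any event on which the two rules differ.

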1. STUDY SYNOPSIS

CLINICAL STUDY SYNOPSIS:	
Study Code	REP0122
Title of Study	Phase 2, proof-of-concept, randomized, double-blinded, placebo-controlled, multicenter study to assess efficacy and safety of reparixin as add-on therapy to standard of care in adult patients with Acute Respiratory Distress Syndrome (RESPIRATIO)
Short title	Reparixin in Acute Respiratory Distress Syndrome (ARDS)
IND/EudraCT No.	161827/2022-001612-25
Study Centres (Country)	US, Germany, Italy
Development Phase	Phase 2, proof-of concept study
Objectives	
1. To characterize the efficacy of reparixin in ameliorating lung injury and systemic inflammation and expediting clinical recovery and liberation from mechanical ventilation in adult patients with moderate to severe ARDS ($\text{PaO}_2/\text{FIO}_2$ ratio ≤ 200). Furthermore, to assess the effect of reparixin on systemic biomarkers linked to a hyper-inflammatory ARDS phenotype.
 
2. CCI CCI
 
3. To evaluate the safety of reparixin vs. placebo in patients enrolled in the study.

Design and Methodology	
Phase 2, proof-of-concept, randomized, double-blinded, placebo-controlled, multicenter study.
 
All patients will receive therapy in line with current standard-of-care as it pertains to ARDS management (protocolized ventilator management will be made available to all sites in accordance with currently accepted standard of care). Patients will be randomized (1:1) to either reparixin or placebo. Duration of treatment will be 14 days with the option to extend to 21 days if the patient is still intubated on Day 14.

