On treatment period TEAE	
AE start date is on or after treatment start date and on or before end of treatment date.
 
If AE start date is missing and the AE is considered treatment-emergent, it is considered on treatment TEAE.
 
In case of End of treatment date missing or if last IMP intake is after End of Treatment date, the last IMP intake (instead of the End of Treatment) will be considered.

Follow-up period TEAE	
AE start date is after end of treatment date.
 
In case of End of treatment date missing or if last IMP intake is after End of Treatment date, the last IMP intake (instead of the End of Treatment) will be considered.

PaO2/FiO2 ratio	When the PaO2/FiO2 ratio is not reported in the eCRF (i.e. the value is missing) but the two values for PaO2 and FiO2 are available separately, the PaO2/FiO2 ratio will be derived as ratio between the two values.

Standard/Forms/Template				
Title		Statistical Analysis Plan Template		
Code		Version	Effective Date	Page
PPD		01	29 Aug 2022	60 of 78

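### SAP Table 4 puts every TEAE with a partial onset date in the treatment period, even when the known month and year show that onset was after treatment ended

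*SAP*

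**What the plan says.** Section 8.1 of the SAP divides TEAEs into an on-treatment and a follow-up period and says this is done "according to the available parts of the onset and the end dates (Table 4"). The algorithm is Table 4 of section 11.1.2 (not the seed-number table in section 11.2, which carries the same number).

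Table 4 treats onset dates as follows:

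- **Fully known onset:** "If AE start date > max(Date of last IMP intake, End of Treatment) then 'Follow-up', otherwise 'Treatment' period".
- **Partial onset that must precede treatment**, labelled "Partial, but known components show that it cannot be on or after IMP start date": not a TEAE, so no period is assigned.
- **All other partial onsets**, labelled "Partial, could be on or after IMP start date": the stop date decides whether the event is a TEAE. One period cell then covers known, partial and missing stop dates alike: "If TEAE, then Treatment study period for TEAE occurrence".
- **Missing onset:** the same period rule.

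Table 3 of section 11.1.1 defines the two periods separately. A follow-up TEAE is one where "AE start date is after end of treatment date". The on-treatment default reads: "If AE start date is missing and the AE is considered treatment-emergent, it is considered on treatment TEAE". Table 3 does not mention a partial start date.

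**The concern.** Table 4 uses the known parts of a partial date at one end of treatment only. They can show that an event began before the first dose; they are never used to show that it began after the last one. A month-only onset lying wholly after treatment has no row of its own, so it falls into the general partial-onset row and is labelled as treatment.

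Section 8.1 splits five system-organ-class and preferred-term tables by period: TEAEs, serious TEAEs, adverse drug reactions, TEAEs leading to IMP discontinuation and TEAEs leading to study discontinuation. An event placed in the wrong period adds to the on-treatment column and is lost from the follow-up column. Because Tables 3 and 4 give different answers for the same record, two programmers working from the same SAP could also produce different tables.

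**Working it through.** The plan gives no figure to reproduce. The check applies the rules as written to concrete dates.

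**Inputs.** Treatment length, from the Protocol synopsis: "Duration of treatment will be 14 days with the option to extend to 21 days" (the extension applies if the patient is still intubated on Day 14). Participation runs to Day 60 (SAP 3.1). The period boundary is the later of last IMP intake and End of Treatment (Table 4, known-onset row); the substitution rule in Table 3 amounts to the same boundary. The IMP start date of 10 January 2024 is assumed for illustration.

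**Dates.** The last treatment day is start + (length − 1), and Day 60 is start + 59.

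- 14-day course: 10 January + 13 = 23 January
- 21-day course: 10 January + 20 = 30 January
- Day 60: 10 January + 59 = 9 March

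**Rules applied to a month-only onset with a missing stop date.** The earliest possible onset is the first of the month. The results are the same for both course lengths.

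| Recorded onset | Earliest possible onset | Table 4 as written | With a check against end of treatment |
|---|---|---|---|
| December 2023 | 1 December | not TEAE | not TEAE |
| January 2024 | 1 January | Treatment | Treatment |
| February 2024 | 1 February | Treatment | Follow-up |
| March 2024 | 1 March | Treatment | Follow-up |

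The February and March rows show the fault. Every possible onset day is after 23 or 30 January, so Table 3 makes these follow-up events, yet Table 4 returns treatment. The January row is ambiguous, and treatment is retained under either rule.

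**How often a month alone would settle the question.** For each IMP start date in 2024, count the days from the end of treatment to Day 60 whose calendar month begins after the last treatment day, and divide by all post-treatment days.

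- 14-day course: 60 − 14 = 46 post-treatment days; average share 68%, range 35% to 100% by start date.
- 21-day course: 60 − 21 = 39 post-treatment days; average share 62%, range 23% to 100%.

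For the 10 January start and a 14-day course, 8 of the 46 days fall in January, 29 in February and 9 in March, giving (29 + 9)/46 = 83%.

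These shares describe the calendar, assuming month-only dates and onset spread evenly over post-treatment days. They show that the situation is not a rare corner of the calendar. They do not estimate how many events will be misplaced.

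**The case against.** Assigning an uncertain onset to treatment is a common conservative convention, and section 8.1 names Table 4 as the place where the rule is set. That defence stands for ambiguous dates, such as January above. It does not cover a date whose known parts rule treatment out, because nothing about the period is then uncertain. Table 3 extends the default to missing dates only.

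The consequences are also limited. Every by-period table has an overall presentation. The overview, severity, death and secondary-infection summaries are not split by period. The rule is the same in both arms, and safety is summarised descriptively. Listings print incomplete dates with dashes (SAP 9.4), so the known month stays visible. An event leading to IMP discontinuation would rarely start after treatment ended, so that table is little exposed. All of this stands.

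A reader might infer that late events reported at the Day 60 phone call will in general appear as on-treatment. The documents do not support this: Table 4 sends any fully dated event after the boundary to follow-up.

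A reader might also take the post-treatment share of the 60 days, 46/60 = 77% or 39/60 = 65%, as the size of the problem. It measures elapsed time, not misassignment, and includes days with planned contact: assessments every 48 hours after extubation until Day 28 or discharge, and a Day 28 visit or call for patients discharged earlier. The stretch without scheduled contact starts at the later of Day 28 and discharge, so it is at most 60 − 28 = 32 days.

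Nor do the documents show that partial dates will cluster among late events. Phone recall makes it plausible, but the eCRF asks for onset and resolution dates (Protocol 8.3), edit checks query completeness (11.2), and serious events are followed until queries are resolved (8.3.1).

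**Conclusion.** The point holds in a narrow form. As written, Table 4 never returns follow-up for a partial onset date, and this contradicts both the Table 3 definition and the principle stated in section 8.1. Nothing elsewhere in either document overrides it.

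The events affected are TEAEs with a partial onset date whose known components place onset after the later of last IMP intake and End of Treatment. Only their period label is wrong. The number of such events cannot be derived from the documents, so the effect on the by-period tables is unknown and may be small. This is a minor inconsistency, worth correcting because the correction is nearly free.

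**What to change.** In the Table 4 rows for a partial onset that could be on or after IMP start, replace the single period instruction with: if the event is a TEAE and the earliest onset date consistent with the known components is after the later of last IMP intake and End of Treatment, assign follow-up; otherwise assign treatment. The conservative default for ambiguous dates is kept. Table 5 already imputes partial medication start dates to the earliest possible date, so the SAP has a precedent for this step.

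Align Table 3 by adding the partial-date case to both period definitions. Section 8.1 then needs no change.

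The cost is one line in Table 4, a short addition to Table 3 and one condition in the adverse-event derivation program. Data collection and clinical procedures are untouched.
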